For patients with a chronic elevation or an acute myocardial injury before surgery, a new myocardial injury after surgery requires identification of a new elevated troponin after surgery as per points 1-5 above, and the troponin elevation must be a 20% rise beyond the chronic troponin value or beyond the last measurement of the acute preoperative myocardial injury that was clearly demonstrated to have peaked and was coming down. Patients meeting diagnostic criteria for MINS will be evaluated for myocardial infarction with EKG and ECHO with cardiac consultation, which will help us detect all infarctions and increase the baseline incidence.

**Secondary outcomes** will include:

- 1) 30-day deep or organ-space surgical site infection, as defined by Center for Disease Control criteria\*;
- 2) Intraoperative transfusion requirement, defined as units of red blood cells transfused;
- 3) Duration of hospitalization (censored at 30 days);
- 4) Readmission within a month of surgery;

Exploratory outcomes will be:

- 1) Estimated intraoperative blood loss;
- 2) The change in blood hemoglobin from preoperatively to the first postoperative morning;
- 3) 30-day superficial surgical site infection;
- 4) Quality-of-recovery 15 on the third postoperative day in person or by phone in patients already discharged;
- 5) 30-day myocardial infarction meeting requirements of the Third Universal Definition.

\*Definitions of surgical site infections, modified from 1990 CDC criteria: <http://www.cdc.gov/hicpac/SSI/table1-SSI.html>.

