## Statistical Plan

Reported temperatures will include time-weighted average, minimum, and final intraoperative core temperatures.

Analyses will be modified intent-to-treat, including all randomized patients who received treatment (i.e., patients randomized but not receiving treatment will not be included in any analyses). Randomized groups will be compared on baseline and demographic characteristics using absolute standardized difference, defined as the absolute difference in means, mean ranks, or proportions divided by the pooled standard deviation. All analyses will adjust for any imbalanced baseline characteristics between randomized groups, defined as the maximum of 0.10 and absolute standardized difference  $> 1.96 \times \sqrt{\frac{1}{n_1} + \frac{1}{n_2}}$ .

Missing outcomes will be imputed using an appropriate method, after examining the missing mechanism and drop-out rates. If less than 5% of data are missing, we will assign worst outcome to the active treatment group and best outcome to the control group for patients missing all records of MINS, non-fatal cardiac arrest and mortality; we will apply the last observation carried forward (LOCF) method for patients missing 30-day follow-up data but having discharge assessment. If missing is 5~20%, we will use the multiple imputation method.

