### **Sample-size Estimate**

[figure not shown]
Amongst 10,000 patients enrolled in POISE-2, 8,449 met the inclusion criteria proposed for PROTECT. The incidence of MINS, nonfatal cardiac arrest, and total mortality within 30 days post-operatively were 10%, 0.1% and 1% respectively. These studies were largely conducted outside the United States and we can thus assume that most patients were either unwarmed or inadequately warmed. We will thus assume that patients assigned to routine management will have a similar incidence of our composite outcome.

A total of 4000 patients will give a power of 0.9 at the 0.05 significance level to detect a 30% or more relative reduction in the primary outcomes, comparing routine

thermal management group to aggressive warming group. Sample size was calculated for common effect GEE model with unstructured covariance matrix, assuming a correlation of 0.1 between outcomes. We estimated sample size using the MULTBINPOW SAS macro [Mascha EJ Power Calculation for Tests on a Vector of Binary Outcomes], which can estimate the power for multivariate GEE model given varying correlation and sample size.

After accounting for interim analysis at each 25% of the maximum enrollment (3 interim analyses and a final analysis, as needed), a maximum of 4802 patients would be needed (2401 per group) for the analysis.

For the primary analysis, we will use a group sequential design with a nonbinding beta boundary, employing a gamma spending function with parameter gamma of -4 for efficacy and 0 for futility, thus spending beta (for futility monitoring) considerably faster than alpha (for efficacy monitoring). Boundaries for efficacy (futility in parentheses) at the each interim and final analyses are  $P \leq 0.001$  ( $P > 0.880$ ),  $P \leq 0.005$  ( $P > 0.525$ ),  $P \leq 0.014$  ( $P > 0.169$ ), and  $P \leq 0.044$  ( $P > 0.044$ ), respectively, based on an anticipated 30% treatment effect. Figure 1 shows the z-statistic boundaries for efficacy and futility at each interim look.

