**Table 1. Expected Cumulative Stopping Probabilities.**

Effect	Expected Stopping Stage	Stopping Probabilities			
		Stage 1	Stage 2	Stage 3	Stage 4
Null	2.48	0.121	0.526	0.872	1.000
½ Null, Alt	2.89	0.093	0.345	0.675	1.000
Alternative	2.64	0.109	0.437	0.812	1.000
Alt X 1.5	1.86	0.315	0.836	0.988	1.000

In addition to the planned 4,802 patients, we will enroll an additional 250 patients to accounting for an expected maximum 5% dropout rate (lost to follow-up and failure to receive any treatment). Therefore, we anticipate to enroll a maximum of **5,052 patients in total**. We also plan six pilot patients at each study site to confirm feasibility before beginning to randomize subjects.

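### Below 5% missing, carrying discharge status forward codes unobserved readmissions and late infections as non-events; the bias is small unless loss differs by arm

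*Combined protocol and SAP*

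**What the plan says.** The missing-data paragraph of the Statistical Plan opens generally: "Missing outcomes will be imputed using an appropriate method, after examining the missing mechanism and drop-out rates". It then sets tiers.

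- **Lowest tier** ("If less than 5% of data are missing"). For patients with no record of any primary component, "we will assign worst outcome to the active treatment group and best outcome to the control group". After a semicolon in the same sentence, "we will apply the last observation carried forward (LOCF) method for patients missing 30-day follow-up data but having discharge assessment".
- **Middle tier.** "If missing is 5~20%, we will use the multiple imputation method".

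The LOCF clause names no outcome. No other missing-data rule is given for the secondary outcomes.

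The secondary outcomes under Measurements include deep or organ-space infection over 30 days and "Readmission within a month of surgery". The Time Line schedules the infection survey at discharge and day 30 and has no row for readmission. The text below Table 1 allows for an "expected maximum 5% dropout rate (lost to follow-up and failure to receive any treatment"), so the lowest tier is the one the plan expects to use. The only robustness analysis named, under Secondary analyses, is a per-protocol analysis of the primary outcome.

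**The concern.** Readmission cannot occur before discharge. If discharge status is carried forward for this outcome, the only value it can give is no readmission, whatever happened to the patient. Infection differs in degree: events recorded by discharge are kept, but one that arises later in a patient not reached at day 30 is coded absent. A death after discharge is likewise coded as survival, which touches the primary composite and not the secondary outcomes.

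Two of the four secondary outcomes are therefore exposed. Their rates would be understated, and unequal loss between arms would show up as a treatment difference. Nothing named in the plan would reveal the effect on these two outcomes. The two halves of the sentence also differ in conservatism: patients with no primary-outcome record are imputed against warming, while partly followed patients are coded event-free after discharge in both arms.

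**Working it through.** **Inputs from the documents.** Analysed number: "a maximum of 4802 patients would be needed (2401 per group) for the analysis". Dropout: at most 5%, with 250 added patients and a maximum of 5,052. Secondary alpha: 0.0125 each (Exploratory analyses). The documents give no rate for readmission or infection, so those below are assumptions. The 30% relative reduction is borrowed from the primary outcome as an illustration.

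**1. The plan's own figure.** 4,802 / 0.95 = 5,055, and 4,802 × 1.05 = 5,043 (rounded up). The stated 4,802 + 250 = 5,052 agrees with both; 250 / 5,052 = 4.95%.

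**2. Ceiling on the patients and events affected.** 0.05 × 5,052 = 253 patients.
- Readmissions, at an assumed rate of 5–10%: 253 × 0.05 = 13 to 253 × 0.10 = 25 coded as non-events.
- Late deaths, at an assumed post-discharge mortality of 0.3–0.5%: 253 × 0.003 = 0.8 to 253 × 0.005 = 1.3, so about one.

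These are upper bounds. The 5% includes patients who receive no treatment, who are excluded from all analyses, and patients with no primary-outcome record fall under the other rule.

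**3. Equal loss in both arms.** Let m be the proportion lost, k the risk of lost patients relative to followed patients, and f the share of events after discharge (f = 1 for readmission). Then

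observed rate = p × [1 − f × km / (1 − m + km)].

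Take m = 4.99% and assumed readmission of 10% versus 7% (relative risk 0.70, difference 3.00 points).

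| Lost patients' risk | Share of events erased | Observed rates | Relative risk | Difference |
|---|---|---|---|---|
| Same (k = 1) | 4.99% | 9.50% vs 6.65% | 0.70 | 2.85 points |
| Three times (k = 3) | 0.1497 / 1.0998 = 13.6% | 8.64% vs 6.05% | 0.70 | 2.59 points |

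In the first row about 20 of 408 events are erased: 2,401 × 0.17 = 408, and 408 × 0.0499 = 20.

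For infection at an assumed 3% versus 2.1%, with half of events after discharge (f = 0.5) and k = 1, about 3 of 122 events are erased (2,401 × 0.051 = 122; 122 × 0.0499 × 0.5 = 3). The relative risk stays at 0.70.

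Power for readmission at 10% versus 7%, alpha 0.0125 and 2,401 per arm is 0.891 with full data, 0.870 with LOCF and 0.872 with complete cases.

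**4. Unequal loss, no true effect.** Assume 6% loss in one arm and 3% in the other (average 4.5%, so still in the lowest tier), with k = 1. The false difference is p × (0.06 − 0.03). With s0 and s1 the pooled and unpooled standard errors, d the false difference and z = 2.50, the rejection probability is Φ((d − z·s0)/s1) + Φ((−d − z·s0)/s1).

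| Assumed readmission | Observed rates | False difference | Standard error | Ratio | Type I error (nominal 0.0125) |
|---|---|---|---|---|---|
| 5% | 4.70% vs 4.85% | 0.15 points | 0.62 points | 0.24 | 0.015 |
| 10% | 9.40% vs 9.70% | 0.30 points | 0.85 points | 0.35 | 0.018 |

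With equal loss, d = 0 and type I error stays at 0.0125.

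**The case against.** **Scope.** The LOCF clause shares a sentence with a rule about the three primary components. It can be read as the second half of a scheme for the primary composite alone. It can also be argued that readmission has no discharge observation to carry forward, so the rule is undefined for it. Both readings are possible, and a reader should not infer that the plan explicitly sets readmission to no. Neither reading removes the problem: each leaves infection, readmission or both with no specific rule below 5% missing.

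**Discretion and effort.** The opening sentence allows the method to be chosen after looking at the data, and day-30 contact attempts run to day 35. The longer contact window should reduce loss. The discretion counts for less, because a definite rule follows immediately.

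**Tiering.** A simple method for little missing data and multiple imputation for more is common practice. That is fair in general, but readmission has the same structural problem on both sides of 5%.

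**Stronger readings that the documents do not support.**
- *The secondary comparisons are biased as the plan stands.* With equal loss the relative risk and type I error are unchanged. The documents neither report nor exclude differential loss.
- *Standard errors are seriously too small.* With equal loss there are no excess false positives, and power is almost the same as with complete cases.
- *The primary result is at risk.* About one death is missed. Myocardial injury, assumed at 10% against 1% for death, is screened on the first two postoperative days and is hardly touched.
- *All secondary outcomes are affected.* Intraoperative transfusion, hospital stay and infections recorded by discharge are not.

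**Conclusion.** The concern holds in limited form: a cheap improvement of minor severity. Read under the paragraph's general opening, the rule for the expected level of missing data turns unobserved readmissions and unobserved post-discharge infections into non-events. Its coverage of these outcomes is inferred from that opening and is not stated.

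The understatement of rates is at most about 5% relative when loss is unrelated to outcome. It is about 14% for readmission if lost patients carry three times the risk. The unchanged relative risk under equal loss assumes that lost patients' excess risk, and the share of events after discharge, are the same in both arms. Bias in the comparison requires loss that differs by arm, and at an assumed 6% versus 3% it is modest. All readmission, infection and post-discharge death rates used here are assumptions.

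**What to change.** In the Statistical Plan:

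1. State which outcomes the LOCF clause covers.
2. For patients with a discharge assessment but no day-30 contact, impute 30-day readmission, deep or organ-space infection and post-discharge death with the multiple imputation already planned for 5–20% missing, whatever the percentage missing. Condition on arm, site, baseline risk and in-hospital events. Keep events recorded by discharge as observed.
3. Do not carry readmission status forward in the main analysis.
4. Report the number without day-30 follow-up by arm.
5. Keep LOCF only as a sensitivity analysis.

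The cost is a change of wording, one extra imputation run and slightly wider intervals. Data collection does not change. Multiple imputation removes the systematic bias only if data are missing at random given the variables in the model, which is why loss by arm should be reported beside it.

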### *Primary analysis*

We will assess the effect of warming strategy on the binary-event composite of myocardial injury, non-fatal cardiac arrest, and all-cause mortality within 30 days of surgery, using a multivariate generalized estimating equations (GEE) method. A common effect GEE test with an unstructured working correlation matrix will be performed, assuming that each component is similarly affected by intervention. The treatment-by-component interaction will be examined in a separate distinct effects GEE model to assess the heterogeneity of the treatment effect across outcomes.

Secondly, we will estimate the average relative effect of aggressive warming across the three categories of complications, using a GEE 'distinct effects' model with an unstructured working correlation matrix. This method is not driven by component with the highest frequency but may have a lower power compared to common effects model because one complication has a lower expected incidence. Regardless of the existence of the interaction, we will report the treatment effect of aggressive warming for each complication. The significance criterion will be 0.017 for each association (i.e., 0.05/3, Bonferroni).

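### The distinct-effects GEE gives non-fatal cardiac arrest, with 4–5 expected events, its own effect, and the plan has no rule for an arm without arrests

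*Combined protocol and SAP*

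**What the plan says.** The *Primary analysis* section tests the composite with a common-effect GEE and then adds a distinct-effects GEE with an unstructured working correlation. Three results come from the second model:

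- **Average.** "we will estimate the average relative effect of aggressive warming across the three categories of complications". It is offered as a summary that the most frequent component does not dominate.
- **Heterogeneity check.** "The treatment-by-component interaction will be examined in a separate distinct effects GEE model". The form of the test (Wald or score) is not named.
- **Component effects.** These are reported whatever the interaction shows. "The significance criterion will be 0.017 for each association", that is, 0.05/3.

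The section's only remark on rarity is that this method "may have a lower power compared to common effects model because one complication has a lower expected incidence". The planning rates are in *Sample-size Estimate*: "The incidence of MINS, nonfatal cardiac arrest, and total mortality within 30 days post-operatively were 10%, 0.1% and 1% respectively", "assuming a correlation of 0.1 between outcomes", with 2,401 patients per group.

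Neither the opening of *Statistical Plan* nor the analysis sections after it say what happens if a component has no events in one arm. They name no penalised or exact method and no minimum event count. *Primary analysis* does not say whether standard errors are robust or model-based.

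**The concern.** Low power and a non-existent estimate are different problems, and the plan mentions only the first. If one arm has no arrests, the arrest log odds ratio is infinite, and so is any average that gives it one third of the weight. A Wald interaction statistic built on it is not defined either.

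The average is the plan's guard against a conclusion driven by MINS, which is planned to be ten times as frequent as death. The interaction is its check on heterogeneity. If either fails at the final analysis, the repair would be chosen with the data in view, or a printed number with no meaning could be reported.

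**Working it through.** **Inputs.** From *Sample-size Estimate*: routine-arm rates of 10% (MINS), 0.1% (non-fatal arrest) and 1% (death); a 30% relative reduction; correlation 0.1; 2,401 per arm. From *Adaptive Design Option*: a cap of 10,000, so 5,000 per arm. Assumed here, because the documents give the arrest rate to one significant figure: a sensitivity range of 0.05–0.15%.

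**1. The plan's own sample size.** A four-look design with the stated spending functions (gamma −4 for alpha at 0.025 per side; gamma 0 for beta of 0.10; non-binding futility) has an inflation factor of about 1.191. Applied to 4,000 this gives about 4,766, against the stated 4,802, a difference under 1%. The stated figure is used below.

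**2. Expected arrests.** No effect: 2 × 2,401 × 0.001 = 4.8. With a 30% reduction: 2,401 × (0.001 + 0.0007) = 4.1.

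**3. Chance that at least one arm has none.** For each arm P0 = (1 − p)^n, and P(at least one empty) = P0C + P0W − P0C × P0W, with C for control and W for warmed.

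- Control: 0.999^2401 = 0.0905.
- No effect: 0.0905 + 0.0905 − 0.0905² = 0.173.
- 15% reduction: warmed arm 0.99915^2401 = 0.130; at least one empty 0.209.
- 30% reduction: warmed arm 0.9993^2401 = 0.186; at least one empty 0.260.

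| Setting | No effect | 30% reduction |
|---|---|---|
| 2,401 per arm, 0.1% | 17.3% | 26.0% |
| 2,401 per arm, 0.05% (assumed) | 51.1% | 60.3% |
| 2,401 per arm, 0.15% (assumed) | 5.4% | 10.5% |
| 5,000 per arm, 0.1% | 1.3% | 3.7% |

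**4. What a fit prints with an empty arm.** Without covariates the distinct-effects model is saturated, so its solution is the three two-by-two log odds ratios, whatever the working correlation. With an empty arm there is no finite solution, and the printed value depends on where iteration stops.

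The robust standard error need not reveal this. If the fitted risk in the empty arm is e, the model-based information is about n·e and the empirical variance of the score is n·e², so that arm adds only n·e²/(n·e)² = 1/n to the variance. With two arrests in the other arm, Var(arrest) ≈ 1/2.

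Test data had 240 MINS and 24 deaths in each arm, fitted in Python statsmodels with unstructured correlation:

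- **Arrests 0 warmed, 2 control:** reported as converged; average log OR about −8.5 to −10.2 depending on the run, robust SE 0.26. That is an overwhelming benefit in print, from two events. The model-based SE was above 10,000, so not significant.
- **Arrests 2 warmed, 0 control:** also reported as converged, but the robust SE of the average was undefined or in the thousands and above, so unusable.
- **Arrests 3 warmed, 2 control:** average +0.14, SE 0.32, an ordinary result.

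**5. The average when it is finite (30% reduction).** Log ORs are −0.389 (MINS), −0.357 (arrest) and −0.360 (death), mean −0.369. The variances are 0.0110, 1.0123 and 0.1020, sum 1.1253.

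- Independent components: SE = √1.1253 / 3 = 0.354; arrest share 1.0123/1.1253 = 90%; power Φ(0.369/0.354 − 1.96) ≈ 18%.
- Correlation 0.1: twice the covariances adds 2 × 0.1 × (0.105×1.006 + 0.105×0.319 + 1.006×0.319) ≈ 0.092. SE = √1.217 / 3 = 0.368; share 83%; power 17%. This is an upper figure for the SE, because the largest attainable MINS–arrest correlation at these rates is 0.095.

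**6. Simulation, 400,000 trials per setting.** With a 30% reduction, the unpenalised average was finite and significant in about 6% of trials. Adding 0.5 to each cell, a simple unadjusted Firth-type penalty, kept it finite every time and gave power of 9.8–9.9%. Under no effect it rejected in 0.6–0.7%.

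**7. What is not affected.** The common-effect GEE stayed finite in all 735 simulated trials with one empty arm. Given one empty arm, it rejected in 4.2–5.3% of no-effect trials. The MINS and death effects do not use arrests.

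**The case against.** The strongest reply is that only the absence of a finite estimate is established. False significance is not. The caption of Figure 1 names SAS and R, and neither was tested. The fits in statsmodels report convergence because that program stops on the size of the score, while the arrest coefficient is still drifting. This stands. What another program prints is unknown; that no finite estimate exists does not depend on the program.

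A reader might infer that the supportive tests therefore have a false-positive rate close to the empty-arm frequency, near 17%. The documents do not support that. It needs robust standard errors, a Wald test, software that gives no warning, and an analyst who reports a log odds ratio near −25 or −30 at face value. The plan names neither robust errors nor a Wald test, model-based errors gave no significance from this cause, and an empty control arm often gave no usable standard error.

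The missing-data rule may also change the picture. When under 5% is missing and all records are absent, "we will assign worst outcome to the active treatment group and best outcome to the control group". If that means imputing arrests in the warmed arm, only an empty control arm matters (0.0905, about 9%), and the SE, share and power figures above no longer apply. The wording does not settle this.

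Two further points stand in part. The plan does disclose lower power, though without a figure and without mentioning non-existence. It also cites methods papers for this GEE approach, whose handling of sparse events cannot be seen from the documents.

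**Conclusion.** The point holds for the supportive analyses and should be corrected. At the plan's 0.1% arrest rate and 2,401 per arm, 17% (no effect) to 26% (30% reduction) of full-size analyses would have no finite arrest odds ratio, three-component average or Wald interaction statistic. The range is 5–60% if the true rate is 0.05–0.15% (an assumption made here), and 1–4% at the 10,000 cap. These figures are for observed events without imputation. When the average exists it is mainly a noisy reading of arrest, with 17–18% asymptotic power.

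A reader might also infer that the trial's primary conclusion is at risk. It is not, because the common-effect test does not estimate an arrest effect separately.

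**What to change.** Revise *Primary analysis* as follows:

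1. Report non-fatal arrest as counts by arm with an exact confidence interval and no GEE p-value. Restate the 0.05/3 criterion to match: either keep 0.017 for MINS and death, or declare 0.05/2 = 0.025.
2. Use a penalised (Firth-type) estimate for the three-component average in every analysis, so that the method does not switch on seeing the data. Name an implementation that can carry the commitment that "All analyses will adjust for any imbalanced baseline characteristics between randomized groups", and state the type of standard error.
3. Do not use a Wald interaction test. A score test rejected in about 4% of no-effect trials overall, but in 12–16% of those with one empty arm. Label the interaction result descriptive whenever a component has no events in an arm.
4. State that the average has low power: about 10% for a 30% reduction, penalised and unadjusted, by simulation.

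The composite, the common-effect test and the sample size stay as they are. The cost is SAP wording and modest programming. The arrest effect within the average is shrunk towards zero, and a less favourable power is on record. The 10% figure was not checked with covariate adjustment.
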